6 POSTOPERATIVE ANALYSIS: OTHER ENDPOINTS

6.1 MONOCULAR CONTRAST SENSITIVITY: MESOPIC WITH AND WITHOUT GLARE AT 1.5, 3, 6 AND 12 CPD AND PHOTOPIC WITHOUT GLARE AT SPATIAL FREQENCIES 3, 6, 12 AND 18 CPD

Spatial frequency testing is to be performed twice under each lighting condition. The average of the two log testing scores will be used for the analysis. If a subject cannot detect the reference pattern in one test and can detect the reference pattern or better in the other test, the score of the other test will be used. For eyes that cannot see the reference pattern for a spatial frequency, the corresponding reference patterns (scores of "0") will be tabulated and presented. Means and medians will be labeled as "<" with the standard deviation labeled as ">" to the reported values as appropriate. A non-parametric analysis of the paired change in contrast sensitivity from

preoperative to the refractive stability point will be conducted in which medians will be provided as valid, unbiased estimates of the center of the distribution; additionally, the 25th and 75th percentile values will be provided to show non-parametric measures of variability. The 95% confidence interval of the median change will also be provided.

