To measure monocular contrast sensitivity using the CSV-1000E chart, subjects are to identify which circle in each vertically-aligned circle set (1-8) contains the sine-wave pattern. The reference pattern for each spatial frequency is provided under the spatial frequency designation (A, B, etc.) on the chart. A similar pattern appears in either the top or bottom of each paired circle set, getting fainter and harder to see with each subsequent circle set. Subjects should be instructed to identify whether the top circle, bottom circle, or neither circle in each circle set contains the pattern. The subject should be prompted until no difference can be determined between the two circles in each set. Any incorrect response(s) prior to no difference being detected should be retested. For example, if a subject detects no difference at number 7, but responded incorrectly at number 4, the subject should be retested starting at number 3. After retesting, the number corresponding to the last correct response in a paired circle set is the score for that spatial frequency. If the subject is unable to see the reference pattern under the letter, then the score for that spatial frequency is zero. If the subject is able to see the reference pattern under the letter, but cannot identify any pattern in circle sets 1-8, then the score for that spatial frequency is the spatial frequency designation (A, B, etc.).

Note that the circle sets on the Vector Vision CSV-1000-1.5CPD chart are oriented sideby-side instead of being vertically aligned, so subjects should be instructed to identify whether the right circle, left circle or neither circle contains the pattern for this chart.

17NOV2015/ 3.0 56 PR/STAR-115-MIPS

NOTE: Spatial frequency testing is to be performed twice under each lighting condition. Score sheets must be retained as source documentation.

Mesopic testing without glare should be performed first, followed by mesopic testing with glare and lastly photopic testing without glare.

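### SAP 6.1 drops a failed contrast sensitivity run, so with the same other run above the reference level, an eye that failed once outscores one that saw only the reference pattern (low priority)

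*SAP*

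**What the plan says.** SAP section 6.1 states: "Spatial frequency testing is to be performed twice under each lighting condition". The default score is the mean of the two runs: "The average of the two log testing scores will be used for the analysis". There is one exception. If the reference pattern is missed in one run but the subject "can detect the reference pattern or better in the other test, the score of the other test will be used".

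Protocol Appendix N fixes the order of the lowest results. A missed reference pattern is the bottom outcome: "If the subject is unable to see the reference pattern under the letter, then the score for that spatial frequency is zero". One rung up, a subject who sees the reference pattern but "cannot identify any pattern in circle sets 1-8, then the score for that spatial frequency is the spatial frequency designation", that is, the letter level. That is a valid score and enters the average.

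SAP section 6.1 also tabulates eyes that cannot see the reference pattern as zeros, and marks means and medians with '<' where appropriate. The outcome is described as "A non-parametric analysis of the paired change in contrast sensitivity from" the preoperative visit to the stability point, reported as a median with quartiles and a 95% confidence interval. Neither document gives a reason for the exception or a sensitivity analysis of it.

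**The concern.** The exception removes the worst possible run and keeps the second worst. A reference-level run stays in the average and pulls the score down; a failed run disappears and pulls nothing down. For a given other run above the reference level, failing is therefore rewarded compared with just seeing the reference pattern. An eye that fails once is also scored exactly as if it had repeated its better run.

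This happens at the floor of the scale, where a postoperative loss would show. If one-run failures become more common after surgery, the paired change looks better than it should. Medians do not protect against this by design. They tolerate floor values that stay at the bottom of the ranking, but here the eye is moved up the ranking.

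**Working it through.** **The plan's related figure.** The scoring rule has no figure of its own. The only number nearby is the substudy power in SAP section 9 and Protocol section 20.6: 65 eyes, one-sided 0.05, margin 0.15, SD of differences 0.40, expected difference 0, power over 90%. Normal approximation: 0.15 × √65 / 0.40 = 3.023; 3.023 − 1.645 = 1.378; Φ(1.378) = 91.6%. The noncentral t with 64 df gives 91.1%. The stated power reproduces, and the scoring rule does not affect it.

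**Ordering of two eyes.** Let R be the log score at the reference level and x the other run, the same for both eyes.

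- Failed once: score = x.
- Saw only the reference pattern in that run: score = (R + x)/2.
- Difference: x − (R + x)/2 = (x − R)/2, positive whenever x > R and zero when x = R.

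**All levels.** Code the scale as 0 for reference only and 1 to 8 for the circle sets. Compare (fail, k), which scores k, with (j, k), which scores (j + k)/2, for every j and k from 0 to 8. Of the 81 comparisons, 36 are inverted (every j < k), 9 tie (j = k) and 36 are correctly ordered (j > k).

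**Per-eye excess.** The documents give no log value per level, so the step s is an assumption. With the other run k levels above reference, the excess over the eye that saw the reference pattern is k × s / 2:

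| Step s (assumed) | k = 1 | k = 2 | k = 4 |
|---|---|---|---|
| 0.10 | 0.05 | 0.10 | 0.20 |
| 0.15 | 0.075 | 0.15 | 0.30 |
| 0.20 | 0.10 | 0.20 | 0.40 |
| 0.30 | 0.15 | 0.30 | 0.60 |

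**Group effect on the mean change.** If an extra share f of eyes fails one run after surgery, the mean change is too favourable by f × k × s / 2, relative to setting the failed run at the reference level. For s from 0.10 to 0.20 and k from 2 to 4:

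- f = 5%: 0.005 to 0.02 log.
- f = 10%: 0.10 × 2 × 0.10 / 2 = 0.01 to 0.10 × 4 × 0.20 / 2 = 0.04 log.
- f = 20%: 0.02 to 0.08 log.

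If one-run failures are the same at both visits, in frequency and in how far the other run lies above reference, the effect cancels.

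**Simulations under assumed values.**

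- Eyes near the floor (step 0.10 to 0.20, test-retest SD 0.15 to 0.20, true loss 0.15 to 0.30): 16 to 29% of postoperative eyes had exactly one failed run. Against averaging in a fixed floor value, the mean change moved by up to about 0.02 log in either direction, and the median by zero to one score increment (0.05 to 0.10 log).
- Eyes averaging level 4 to 5 of 8 (step 0.15 to 0.20, test-retest SD 0.15 to 0.20, between-eye SD 0.20, true loss 0.15): 0.1 to 8% had one failed run. Against setting failed runs at the reference level, the mean change moved by at most 0.005 log and the median not at all. With no true change, the bias was zero.

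**Check of the replacement rule.** With the failed run set at the reference level, (fail, k) scores (0 + k)/2, which is never above (j + k)/2. Of the 81 comparisons, 9 tie (j = 0) and 9 × 8 = 72 are correctly ordered. None is inverted.

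**The case against.** A score of zero has no logarithm, so a failed run is left-censored and some convention is needed; the SAP prespecifies one and makes no distinction between visits. A single failure may be a lapse, in which case the other run is the better measurement. Appendix N does guard against misunderstanding, with a trial reading first and retesting of incorrect responses. Failures may also be rare: eyes enter with BSCVA of 20/20 or better, are tested with best correction, and are not tested at 18 cpd under mesopic conditions. The zero tabulation and the '<' label might already expose the affected eyes.

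The points on size stand: the documents do not place eyes near the floor, and the effect may be negligible. The need for a convention also stands, but it does not justify this one, because a censoring convention should not put a failed run above a seen reference pattern. Neither document offers the lapse argument as a reason. It is also not stated that the tabulation or the label covers an eye that failed only one run.

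Three stronger readings are tempting, and the documents do not support them.

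- A reader might infer that any eye failing once outscores any eye that sees the reference pattern. It does not: (fail, reference) ties with (reference, reference) and scores below (reference, level 2).
- A reader might set the per-eye excess against the 0.15 margin. At an assumed step of 0.15, (fail, level 2) scores 0.30 above reference under the SAP, against (−0.15 + 0.30)/2 = 0.075 with a floor one step below reference, a gap of 0.225. But both the step and that floor are assumptions, and the margin applies to a mean over 65 eyes, not to one eye.
- A reader might infer that the rule always hides a loss. The direction depends on how one-run failures differ between visits.

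**Conclusion.** The misordering follows from the text by algebra and needs no assumption beyond an equal other run above the reference level. Its effect on the reported change is small or unknown. It rests on an assumed log step, an assumed failure rate and an assumed difference between visits: about 0 to 0.02 log in the mean in most simulated settings, about 0.04 at the upper end if an extra 10% of eyes fail one run, and zero to one score increment in the median. Contrast sensitivity is listed among the other endpoints (Protocol section 6.2), comes from a single-site substudy, has no success criterion in SAP section 6.1 and is not among the stratified outcomes in SAP section 7. No primary conclusion depends on it. The rule should be corrected, at low priority.

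**What to change.** In SAP section 6.1, replace the sentence on using the other test's score with a rule of this kind: a run that misses the reference pattern is assigned the reference-level log value as an upper bound, averaged with the other run, and the result is flagged with the existing '<' label, at both visits. The reference level is the right value for that label, because a failed run shows only that sensitivity lies below it; a value one step lower would be a guess, not a bound. For the paired change, say which way the bound runs: a flagged preoperative score makes the change a lower bound, a flagged postoperative score an upper bound.

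Tabulate one-run and two-run failures separately by visit, so that any imbalance is visible. A sensitivity analysis with a lower floor value is optional.

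The cost is one or two sentences and one table. No new data are needed, since both runs are recorded and the score sheets are kept. The downside is that reported contrast sensitivity may look slightly less favourable.

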6.2 BINOCULAR UCVA

The frequency and proportion of subjects with each acuity line of binocular UCVA (20/16 or better, 20/20 or better, 20/25 or better, 20/40 or better, 20/100 or better and worse than 20/100) will be summarized over time.

6.3 POSTOPERATIVE UCVA VS. PREOPERATIVE BSCVA

The frequency and proportion of eyes with acuity line changes of UCVA compared to preoperative BSCVA (decreases of >2 lines, =2 lines, =1 line, no change, increases of =1 line, =2 lines and > 2 lines) will be reported over time.

6.4 MANIFEST SPHERE VS. CYCLOPLEGIC SPHERE

Mean, standard deviation, minimum and maximum for manifest and cycloplegic spheres and the paired difference between the manifest and cycloplegic spheres at the pre-operative and at the stability time point will be presented.

The difference between the manifest and cycloplegic refractions is calculated as follows: Cycloplegic and Manifest Sphere Difference = Cycloplegic Sphere - Manifest Sphere

6.5 MANIFEST CYLINDER ANALYSIS

Summary statistics (mean, standard deviation, median, minimum and maximum) will be reported over time for MRC.

6.5.1 NON-VECTOR ANALYSES

Accuracy of Cylinder to Target (Emmetropia)

The accuracy of MRC will be summarized over time. The summary will include the frequency and proportion of eyes MRC within \pm 0.50 D and with \pm 1.00 D. In addition, mean and standard deviation of attempted correction and achieved correction and the percent of achieved correction for MRC will be calculated as follows at each evaluation time point:

- Mean Attempted Correction = Mean of (Preop MRC)
- Mean Achieved Correction = Mean of (Postop MRC Preop MRC)
- % Achieved = [Mean of (Postop MRC Preop MRC)/ Mean of (Preop MRC)] *100

18NOV2015/3.0

Reduction of Absolute Cylinder at Stability Time Point

The reduction of absolute cylinder for astigmatic eyes (preop |MRC| > 0.50 D) will be calculated as follows at the stability time point.

• % Reduction= [Mean of (Preop MRC - Postop MRC)/ Mean of (Preop MRC)] *100

The mean, minimum and maximum of the percent of reduction of absolute cylinder will be presented by preoperative MRC categories (>0.00 D to ≤ 0.50 D, >0.50 D to ≤ 1.00 D, >1.00 D to ≤ 2.00 D, >2.00 D to ≤ 3.00 D, >3.00 D to ≤ 4.00 D).

Absolute Shift in Axis at Stability Time Point

For astigmatic eyes (preop |MRC| > 0.05 D), the frequency and proportion of eyes with absolute shift in axis (0°, > 0 to $\le 5^{\circ}$, > 5 to $\le 10^{\circ}$, > 10 to $\le 15^{\circ}$, > 15 to $\le 30^{\circ}$, > 30°) will be presented by residual cylinder magnitude categories (0.00 D, >0.00 D to $\le 0.50 \text{ D}$, >0.50 D to $\le 1.00 \text{ D}$, >1.00 D to $\le 2.00 \text{ D}$, >2.00 D to $\le 3.00 \text{ D}$, >3.00 D to $\le 4.00 \text{ D}$ etc.) at the stability time point.

Absolute shift in axis is determined as follows:

- If postoperative axis preoperative axis > 90, then axis shift = |postoperative axis preoperative axis 180|.
- In other cases, if postoperative axis preoperative axis <-90, then axis shift = 180 + postoperative axis preoperative axis.
- In other cases, axis shift = |postoperative axis preoperative axis|.
- Shifts are defined to be zero for eyes with zero residual cylinder magnitude.

A listing of eyes with residual astigmatism of greater than 0.50 D and an axis shift of >30° will be provided.

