  - O Cylinder Axis Tolerance: If either the manifest cylinder entered into the iDesign System or the iDesign cylinder selected for treatment is less than 0.5 D, there is no requirement for axis tolerance. When both cylinders have a magnitude of at least 0.5 D, the axis tolerance as determined by the iDesign system is linearly reduced from 15° (0.5 D) to 7.5° (7.0 D) based on the average magnitude of both cylinders. Note: If the axis tolerance is not in the calculated range, the iDesign system will produce a warning and this exam may not be used for treatment planning.
- 11. Willing and capable of complying with follow-up examinations for the duration of the study.

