#### 8.1 INCLUSION CRITERIA

## Inclusion Criteria (all criteria apply to each study eye):

- 1. Signed informed consent and HIPAA authorization
- 2. At least 18 years of age at enrollment (date informed consent signed)
- 3. The refractive error, based on the iDesign displayed refraction selected for treatment ("4.0 Rx calc" at 12.5 mm), must be myopia with or without astigmatism with sphere up to -8.00 D, and cylinder between 0.00 D and -4.00 D with a maximum spherical equivalent (SE) of -10.00 D
- 4. Anticipated residual stromal bed thickness of at least 250 microns as calculated by the iDesign system
- 5. Distance Best Spectacle Corrected Visual Acuity (BSCVA) of 20/20 or better
- BSCVA ≥2 lines (≥10 letters) better than distance Uncorrected Visual Acuity (UCVA)
- 7. Less than or equal to 0.75 D difference between cycloplegic and manifest refraction sphere.
- 8. A stable refractive error (based on a previous exam, medical records, lensometry, or prescription at least 12 months prior to the preoperative manifest refraction), as defined by a change of ≤1.00 D in MRSE.
- 9. Any subject eye with a history of contact lens wear within the last 4 weeks must demonstrate refractive stability according to the following:
  - Rigid contact lenses (toric or spherical) must be removed for at least 4 weeks and soft contact lenses (toric or spherical) for at least 2 week prior to the first refraction used to establish stability.
  - Two consecutive manifest refractions and keratometry readings must be conducted at least 7 days apart.
  - Refractive stability is defined as a change of not more than 0.50 D in manifest refractive sphere and cylinder as well as keratometry meridian (either axis) between measurements.
  - If the subject/eye meets the refractive stability criteria, contact lens wear is not permitted prior to surgery
- 10. Agreement between manifest refraction (adjusted for optical infinity) and iDesign System refraction chosen for treatment, as follows:
  - Spherical Equivalent: Magnitude of the difference is less than 0.625 D.
  - Cylinder: Magnitude of the difference is less than or equal to 0.5 D.

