5.2 PRIMARY SAFETY ENDPOINTS

Maintenance of BSCVA

The frequency, proportion and 95% confidence intervals of eyes with each acuity line of BSCVA (i.e. 20/20 or better, 20/25 or better, 20/40 or better, etc.) will be reported over time. The frequency

and proportion of eyes with BSCVA acuity line changes from preoperative (decreases of >2 lines, =2 lines, =1 line, no change, increases of =1 line, =2 lines and > 2 lines) will be summarized over time.

The success criteria for the endpoints regarding maintenance of BSCVA are achieved if the proportion of eyes with a loss of >2 lines of BSCVA from preoperative is <5%, the proportion of eyes with haze beyond 6 months with a loss > 2 lines of BSCVA is <1%, and the proportion of eyes with BSCVA of 20/20 or better preoperatively and BSCVA 20/40 or worse postoperatively is <1%.

Induced Manifest Refractive Astigmatism

Induced manifest refractive astigmatism is defined as the absolute change in manifest refractive cylinder (MRC) from preoperative. The following formula will be used to determine absolute change in MRC (rounded to the nearest 0.25 increment):

```
Absolute Change in Cylinder = |Preop MRC| - |Postop MRC|
```

The frequency, proportion and 95% confidence intervals of eyes with absolute changes in manifest cylinder from preoperative visit will be summarized in categories (increases of >2.00 D, 2.00 D, 1.75 D, 1.50 D, 1.25 D, 1.00 D, 0.75 D, 0.50 D, 0.25 D, no change, decreases of 0.25 D, 0.50 D, 0.75 D, 1.00 D, 1.25 D, 1.50 D, 1.75 D, 2.00 D, > 2.00 D) at each periodic study visit.

The success criterion is achieved if the proportion of eyes with induced manifest refractive astigmatism of >2.00 D is <5%.

Serious, Device-Related Adverse Events

The frequency and proportion of eyes with serious, device-related adverse events throughout the study will be summarized. The success criterion is achieved if the proportion of eyes with serious, device-related adverse events is <1% cumulatively.

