6.5.2 VECTOR ANALYSES

Vector analysis will be conducted in accordance with Eydelman 2006³ for eyes with astigmatism (magnitude of preoperative MRC >0.50 D).

Vector Stability of MRC

Vector stability of MRC will be evaluated for two cohorts: a "consecutive cohort" (eyes with data at two consecutive visits) and a "consistent cohort" (eyes with data at all periodic visits through the point of stability and the confirmatory time point).

The frequency, proportion and 95% confidence intervals of eyes with vector MRC change \leq 1.00 D, as well as \leq 0.50 D, between visits will be reported. Mean, standard deviation and 95% confidence

³ Eydelman M, Drum B, Holladay J etc (2006). Standardized analyses of correction of astigmatism by Laser systems that reshape the cornea. Journal of Refractive Surgery 22: 81-95.

intervals of the mean magnitude of MRC vector change between visits and the mean MRC vector change per year and mean MRC vector change per month will be calculated and reported.

Vector Analysis Summary at Stability Time Point

The mean and standard deviation of intended refractive change (|IRC|), surgically induced refractive change (|SIRC|), error vector (|EV|), correction ratio (CR) and error ratio (ER) will be presented by preoperative MRC categories (>0.50 D to ≤1.00 D, >1.00 D to ≤ to 2.00 D, >2.00 D to ≤ to 3.00 D, >3.00 D to ≤ 4.00 D).

Error of Magnitude (EM) at Stability Time Point

The mean and standard deviation of EM will be presented by preoperative MRC categories (>0.50 D to ≤ 1.00 D, >1.00 D to ≤ 2.00 D, >2.00 D to ≤ 3.00 D, >3.00 D to ≤ 4.00 D). The frequency and proportion of eyes for each preoperative MRC category will be reported.

Error of Angle (EA) at Stability Time Point

The mean and standard deviation of EA will be presented by preoperative MRC categories (>0.50 D to ≤ 1.00 D, >1.00 D to ≤ 2.00 D, >2.00 D to ≤ 3.00 D, >3.00 D to ≤ 4.00 D). The frequency and proportion of eyes for with $|EA| \leq 15^{\circ}$, EA>+15° and EA $\leq 15^{\circ}$ will also be reported.

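### The axis-shift table in SAP 6.5.1 sets astigmatic eyes at preoperative cylinder above 0.05 D, while the neighbouring analyses use 0.50 D, so it covers a different population

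*SAP*

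**What the plan says.** SAP 6.5.1 contains two consecutive analyses of astigmatic eyes at the stability time point.

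- Reduction of Absolute Cylinder: "The reduction of absolute cylinder for astigmatic eyes (preop |MRC| > 0.50 D) will be calculated as follows at the stability time point". The same paragraph then says results "will be presented by preoperative MRC categories (>0.00 D to ≤ 0.50 D" and upward, a band that its own restriction excludes.
- Absolute Shift in Axis: "For astigmatic eyes (preop |MRC| > 0.05 D), the frequency and proportion of eyes with absolute shift in axis". Results are broken down by residual cylinder, starting with a 0.00 D row. The shift is set to zero when residual cylinder is zero. A separate listing covers eyes with residual astigmatism above 0.50 D and a shift above 30°.

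SAP 6.5.2 runs the vector analyses "for eyes with astigmatism (magnitude of preoperative MRC >0.50 D", and its preoperative category tables, including Error of Angle, begin above 0.50 D.

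SAP 5.2 takes the change in manifest cylinder "rounded to the nearest 0.25 increment". Low-cylinder eyes can be enrolled, because Protocol 8.1 criterion 3 allows "cylinder between 0.00 D and -4.00 D with a maximum spherical equivalent (SE) of -10.00 D". On axis agreement, criterion 10 says that if the manifest cylinder or the "iDesign cylinder selected for treatment is less than 0.5 D, there is no requirement for axis tolerance".

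**The concern.** One term carries two cut-offs that differ tenfold, in adjoining paragraphs, with no explanation. The likeliest cause is a digit slip for 0.50 D. A cut-off of 0.05 D has no natural meaning on a 0.25 D scale, and where the SAP wants any non-zero cylinder it writes above 0.00 D.

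A programmer following the text would build the axis-shift table on every eye with non-zero preoperative cylinder and the vector tables on eyes above 0.50 D. A reader comparing axis shift with Error of Angle would take both to describe the same astigmatic eyes. Axis is less well determined when cylinder is small, so the added eyes can change the picture of rotational alignment for a reason unrelated to the device.

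**Working it through.** **Step 1. Cut-offs side by side.**

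| Analysis | Preoperative cut-off | Lowest class admitted on a 0.25 D scale |
|---|---|---|
| SAP 6.5.1, reduction of cylinder (text) | > 0.50 D | 0.75 D |
| SAP 6.5.1, reduction of cylinder (bands) | > 0.00 D | 0.25 D |
| SAP 6.5.1, axis shift | > 0.05 D | 0.25 D |
| SAP 6.5.2, vector analyses | > 0.50 D | 0.75 D |

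The 0.25 D and 0.50 D eyes are therefore the whole difference between the two definitions. Eyes with zero cylinder stay out under both. That preoperative cylinder is recorded in 0.25 D steps is inferred from SAP 5.2. A finer scale would not change the conclusion, since 0.05 D would still admit nearly all low-cylinder eyes.

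**Step 2. Form of the effect.** Let s be the share of 0.25–0.50 D eyes among those admitted at > 0.05 D, and let r_L and r_H be the proportions shifting more than 30° in the low-cylinder and > 0.50 D eyes.

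- Rate as written = s × r_L + (1 − s) × r_H
- Rate with the 0.50 D cut-off = r_H
- Change = s × (r_L − r_H)

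The documents give none of s, r_L or r_H.

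**Step 3. Illustrative range.** All inputs in this step are assumptions.

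- 70–100% of the cylinder is corrected.
- Residual error is added in double-angle components with SD 0.25 D, 0.35 D, or proportional (0.10 + 0.15 × preoperative cylinder).
- Residual cylinder is rounded to 0.25 D, and the SAP's zero-shift rule is applied.
- Low-cylinder eyes are split equally between 0.25 D and 0.50 D. The others lie between 0.75 D and 3.00 D; changing their mix moves the levels but not the pattern.
- There are 200,000 simulated eyes per cell.

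Percentage shifting more than 30°, with s = 40%:

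| Correction, residual SD | Non-zero residual: > 0.50 D cut-off → as written | All eligible eyes: > 0.50 D cut-off → as written |
|---|---|---|
| 70%, 0.25 D | 15.5 → 28.0 (+12.5) | 14.8 → 26.1 (+11.3) |
| 80%, 0.35 D | 35.6 → 44.9 (+9.3) | 34.1 → 42.7 (+8.6) |
| 90%, 0.25 D | 43.5 → 50.5 (+7.0) | 39.2 → 45.1 (+5.9) |
| 90%, proportional | 49.4 → 52.0 (+2.6) | 45.1 → 43.5 (−1.6) |
| 100%, proportional | 66.9 → 66.8 (about 0) | 60.5 → 55.5 (−5.0) |

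Two of the all-eyes rows by hand:

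- 90%, SD 0.25 D: r_L = (0.56 + 0.52)/2 = 0.54 and r_H = 0.392. Change = 0.4 × (0.54 − 0.392) = +0.059.
- 100%, proportional: r_L = (0.44 + 0.52)/2 = 0.48 and r_H = 0.605. Change = 0.4 × (0.48 − 0.605) = −0.05.

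The sign reverses because of the zero-shift rule. In the last scenario 34% of 0.25 D eyes and 22% of 0.50 D eyes end with zero residual cylinder and count as 0°, against 16% at 0.75 D and 3% at 3.00 D.

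With s = 20% the effects are smaller. The 90% proportional case gives +1.2 points among non-zero residuals (49.4 → 50.6).

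**The case against.** **The table is descriptive and already broken down by residual cylinder.** No pooled rate above 30° is planned. This stands, and it limits the distortion. It does not remove it, because no row filters on preoperative cylinder.

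**The 0.50 D cut-off is not universal.** The cylinder accuracy summary in SAP 6.5.1 and the keratometric axis-shift analysis in SAP 6.6 have no such restriction. True, but neither claims to be limited to astigmatic eyes. Wherever the SAP uses that restriction for manifest cylinder, the cut-off is 0.50 D, apart from this one place.

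**The axis is usable at 0.50 D.** The protocol waives axis agreement only below 0.5 D, and from 0.5 D it requires agreement within 15° or less. This stands: the eyes at exactly 0.50 D cannot be treated as having no meaningful axis.

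**A reader might infer a large, one-directional inflation.** If axis were pure noise in low-cylinder eyes, shifts would be uniform on 0–90° and 60/90 = 67% would exceed 30°. At assumed shares of 20–40% that gives 0.667 × 0.20 = 13 to 0.667 × 0.40 = 27 points. The documents do not support this. It is the gross contribution of those eyes, and it equals the net change only if no eye above 0.50 D shifts by more than 30°. It also ignores the zero-shift rule and the axis requirement at 0.50 D.

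**A reader might also infer that the listing would fill with spurious misalignment.** It would not. The listing already requires residual astigmatism above 0.50 D, so an eye with 0.25–0.50 D before surgery appears only if its cylinder increased. That is worth listing.

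**Conclusion.** The inconsistency is real and visible on the page. As written, the axis-shift table takes in all 0.25 D and 0.50 D eyes, so its population differs from that of the vector analyses it would naturally be read beside. The distribution of shifts can be distorted. Among eyes with non-zero residual cylinder the distortion is usually upward when correction is incomplete. At full correction it vanishes, and over all eligible eyes it can reverse.

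The range of +11 to −5 points over all eyes rests on an assumed 40% share of low-cylinder eyes and on assumed correction and residual error. It shows that the cut-off can matter and predicts nothing about this trial. That 0.05 D is a slip for 0.50 D is the likeliest explanation, but only the sponsor can confirm it.

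The point is minor. This is a descriptive table among the other endpoints, with no success criterion or test attached. No primary endpoint, sample size or alpha changes.

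**What to change.** - In SAP 6.5.1, Absolute Shift in Axis, change the table's cut-off to preoperative |MRC| > 0.50 D. If a separate cut-off was intended, state it on the 0.25 D scale and give the reason.
- If low-cylinder eyes are of interest, show 0.25–0.50 D in a separate row.
- State that the listing (residual cylinder above 0.50 D and shift above 30°) is open to all eyes, whatever their preoperative cylinder. It sits under the same subheading. If the new cut-off were carried over to it, low-cylinder eyes with induced astigmatism would drop out.
- In the reduction table, remove the band from above 0.00 D to 0.50 D, or widen the text restriction so that the two agree.

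The cost is a few words in the SAP before programming, with no new data. The one risk is losing low-cylinder eyes from view, which the separate row and the open listing prevent.
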